3.4 Sample Size

A total of 116 patients will be enrolled from each clinic to measure clinical outcomes over time, for a total sample of 1,160 patients recruited over a two-year period.

Sample size and power: Assumptions. Statistical power analyses are based on these assumptions: (1) two-sided statistical significance tests; (2) Type I error $\alpha=0.05$; (3) power ($1-\beta$) of 80%; (4) intraclass correlation coefficient (ICC) of 0.02 for the mental health outcome. For behavioral interventions, clinic-level ICCs normally range from <<0.01 to 0.04. For effect size, up to 30% of depressive episodes may remit without treatment. We assume that the basic implementation package may improve depression treatment, so we assume the incidence of depression remission to be 40% with the basic package. A difference of 15 percentage points or more in depression remission in the enhanced arm relative to the basic arm would be clinically meaningful and worth detecting. Therefore the study is powered to detect this difference. Based on extremely high retention success in prior studies and the short time frame of the primary outcome (3 months), 90% retention is assumed. Given these assumptions, we will enroll 116 participants per clinic from 10 clinics, or 1,160 participants overall. Fewer clinics would require a prohibitive sample size.

We will also complete qualitative interviews with 8 patients, 6 clinic directors, 6 Clinical Coordinators, 12 providers, 6 Friendship Bench counselors, 6 SHARP research assistants, and 3 MOH officials. These interviews will take place in Year 3 of the study. Given standard sample size guidelines for qualitative data collection, this sample size is expected to be sufficient for theme saturation in each group.

We will additionally conduct 16 cognitive interviews and 200 structured surveys with nurses, clinicians and peer friendship bench counsellors to evaluate providers' perceptions of stigma and acceptance towards individuals with mental health disorders. These

interviews and surveys will take place in Year 3 of the study. The desired sample size for cognitive interviewing, while adequate for the inclusion of variety of staff, reflects the expectation that data saturation will be reached with a relatively small number of participants. The desired sample size for structure interview is reflective of the expectation that approximately 10 participants are needed for every survey item in the measure.

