4.0 STATISTICAL ANALYSIS PLAN

Analysis of implementation and effectiveness outcomes will be intent-to-treat comparisons between arms. Comparisons will be made using generalized estimating equation models with a log link and binomial error distribution to compare proportions. The design effect introduced by clinic-level randomization will be addressed using the bias-corrected robust variance estimate for GEE models recommended given the small number of clusters. A secondary, as-treated analysis will restrict the analysis to those who received a minimum

dose of the depression treatment program (e.g., at least three depression care management appointments).

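### The 80% power in section 3.4 makes no allowance for having only 5 clinics per arm; under the plan's own inputs, power for 40% vs 55% is about 67% (log risk ratio, t on 8 df)

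*Combined protocol and SAP*

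**What the plan says.** Section 3.4 sets out its inputs: "two-sided statistical significance tests", alpha 0.05, power 80%, an ICC of 0.02, remission of 40% in the basic arm, a target difference of 15 percentage points and 90% retention. It then states: "Given these assumptions, we will enroll 116 participants per clinic from 10 clinics, or 1,160 participants overall". Of the 15-point difference it says: "Therefore the study is powered to detect this difference". On the ICC it adds: "For behavioral interventions, clinic-level ICCs normally range from <<0.01 to 0.04". Section 3.0 randomizes clinics 1:1, so there are 5 per arm.

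Section 4.0 gives the analysis: "Comparisons will be made using generalized estimating equation models with a log link and binomial error distribution to compare proportions". Clustering is to be handled with "the bias-corrected robust variance estimate for GEE models recommended given the small number of clusters". It does not say which bias correction is meant, and it gives no reference distribution or degrees of freedom.

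**The concern.** With 5 clinics per arm, the between-clinic variance that drives the test is itself poorly estimated. A valid test has to pay for that, either with a wider reference distribution (t on 8 df, critical value 2.306 instead of 1.960) or with an inflated variance. Section 4.0 accepts the point by prescribing a small-sample correction. Section 3.4 mentions no t quantile, degrees of freedom or extra clinics. If its power comes from normal quantiles, the planned analysis carries a penalty that the power statement leaves out.

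Two things are at stake. First, a null result could be read as excluding a 15-point difference with 80% power, in a trial meant to inform Ministry of Health scale-up. Second, because the test in 4.0 is not fully named, its type I error is open and the choice could be made after the data are seen.

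**Working it through.** **Inputs.** From section 3.4: two-sided alpha 0.05, power 80%, ICC 0.02, 40% vs 55%, 90% retention, 116 enrolled at each of 10 clinics. From section 3.0: 1:1 allocation, so K = 5 clinics per arm. From section 4.0: log link, so the effect is a log risk ratio. Assumed here: t on 10 − 2 = 8 df, equal clinic sizes and no covariate adjustment.

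**1. Reproducing 116.** Section 3.4 names no formula. On the risk-difference scale with unpooled variance and normal quantiles:

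- Effective n per arm = (1.960 + 0.842)² × (0.40×0.60 + 0.55×0.45) / 0.15² = 170.06.
- Solving 5m / (1 + 0.02(m − 1)) = 170.06 gives m = 104.24 analysed per clinic.
- 104.24 / 0.90 = 115.8, that is 116 per clinic and 1,160 in total.

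The other variants tried do not give 116: pooled variance gives 122.3, a continuity correction 158.2, the log risk ratio with z 138.4, and inflating by 1.1 instead of dividing by 0.9 gives 114.7. So the matching calculation uses normal quantiles and has no small-cluster term.

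**2. Power under the same inputs.** Analysed per clinic: 116 × 0.90 = 104.4. Design effect: 1 + 103.4 × 0.02 = 3.068. Effective n per arm: 522 / 3.068 = 170.1.

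- Log risk ratio: ln(0.55/0.40) = 0.3185.
- SE = √[(0.60/0.40 + 0.45/0.55) × 3.068/522] = 0.1167.
- Noncentrality = 0.3185 / 0.1167 = 2.728 (2.802 on the difference scale).

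| Scale | z | t, 8 df (noncentral t) |
|---|---|---|
| Risk difference | 80.0% | 69.1% |
| Log risk ratio | 77.9% | 66.8% |

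Replacing z by t costs about 11 points on either scale; moving from difference to log risk ratio costs about 2.

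**3. Does the result depend on choosing t on 8 df?** Beta-binomial simulation (200,000 runs, 5 + 5 clinics, 104 per clinic, ICC 0.02, log risk ratio). With equal clinic sizes, the robust variance is multiplied by K/(K − 1) = 1.25 for Kauermann-Carroll and by 1.25² = 1.5625 for Mancl-DeRouen. Type I error was taken with both arms at 40% and with both at 55%.

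| Correction and reference | Power, 40% vs 55% | Type I error |
|---|---|---|
| Kauermann-Carroll, t 8 df | 66.6% | 4.8–5.0% |
| Mancl-DeRouen, z | 70.4% | 5.8–6.0% |
| Mancl-DeRouen, t 8 df | 57.6% | 3.2–3.3% |
| Kauermann-Carroll, z | 77.5% | 8.4–8.5% |

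A separate 100,000-run simulation agreed to within half a percentage point. No combination reaches 80%, and the closest clearly exceeds the plan's alpha.

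**4. Detectable difference and ICC.** On the log risk-ratio scale with t on 8 df, 80% power at ICC 0.02 applies to 40% vs 57.7%, or 17.7 points; simulation with Kauermann-Carroll and t gave 80.4% there. Power for 40% vs 55% across the ICC range that 3.4 quotes (0.001 and 0.005 are my assumption for its lower end):

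| ICC | 0.001 | 0.005 | 0.01 | 0.02 | 0.03 | 0.04 |
|---|---|---|---|---|---|---|
| Power | 97.7% | 92.3% | 83.4% | 66.8% | 54.5% | 45.8% |

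80% is reached only at an ICC of about 0.012 or below.

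**5. Could more patients repair it?** As m grows, the effective n per arm tends to 5 / 0.02 = 250. Noncentrality then tends to 3.307 and power to 82.5%. Reaching 80% at these 10 clinics would take about 727 analysed, or 727 / 0.90 ≈ 808 enrolled, per clinic.

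**The case against.** The arithmetic in 3.4 is exact on its own basis, and t on 8 df appears nowhere in 4.0. A reader could say that 67% is the power of a test supplied by the reviewer. Section 4.0 is also compatible with Kauermann-Carroll and z, which gives 77.5%, only 2.5 points short. This stands as far as it goes: the exact power cannot be fixed from the plan, and the documents alone support a range of about 58% to 78%. But the top of that range comes with a type I error of 8.4–8.5% against a stated 5%, and even it falls short of 80%.

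Not all of the fall from 80% to 67% is a small-cluster effect. That is right: about 2 points come from the change of scale, and on the difference scale the penalty alone takes 80.0% to 69.1%.

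The change history shows that the sample size justification entered at version 1.1 (November 2018) and GEE at version 1.9 (November 2022), after the trial period given in section 3.3. The 80% is therefore a design-stage figure. That explains the mismatch, but the current document still claims a power that its current analysis does not have. A null result would indeed be judged mainly on its confidence interval; the width of that interval also depends on the unnamed test.

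Equal clinic sizes and no baseline adjustment are assumed. The first follows from recruiting 116 at every clinic; the second is all that 4.0 specifies. Unequal sizes would lower power, and prognostic adjustment could raise it. Finally, 3.4 attaches the 90% retention to a 3-month outcome, while the hypotheses in 2.1 are at 6 and 12 months. The figures here hold for whichever visit has 90% retention.

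**Conclusion.** The concern holds. The stated 80% is a normal-quantile figure on the difference scale and is not delivered under the plan's own ICC and alpha by the analysis in 4.0. The best single figure is about 67% (log risk ratio, t on 8 df), so the chance of missing a true 15-point difference is about one in three rather than one in five. Among bias-corrected tests with type I error near or below 5%, power is roughly 58% to 71%; the upper end, Mancl-DeRouen with z, has 5.8–6.0%. Leaving the test unnamed lets type I error range from about 3% to 8.5%. These figures rest on 104 analysed patients at each of 10 clinics, ICC 0.02, equal clinic sizes and no covariate adjustment. The conclusion that 80% is not reached does not depend on which of the four tests is chosen.

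**What to change.** In 3.4, keep the derivation of 116 as a record if wished, but replace the 80% claim with wording such as:

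> With 10 clinics (5 per arm), 116 enrolled per clinic, 90% retention and ICC 0.02, the log risk-ratio test in section 4.0 (t, 8 df) has about 67% power for 40% vs 55%; 80% power applies to a difference of about 18 points (40% vs 58%). Power for 40% vs 55% by ICC: 98% (0.001), 92% (0.005), 83% (0.01), 67% (0.02), 55% (0.03), 46% (0.04). Equal clinic sizes and no covariate adjustment are assumed.

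The sentence should also name the visit to which it applies.

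In 4.0, name the matching test, for example:

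> The arm effect will be tested with the Kauermann-Carroll bias-corrected variance and a t reference on 8 df (clinics minus 2).

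If the sponsor prefers another test, 3.4 must give that test's power: for Mancl-DeRouen, about 70% with z or 58% with t on 8 df.

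The cost is a wording change in 3.4 and one sentence in 4.0, with no extra patients or clinics. The stated power becomes less favourable. Fixing t on 8 df gives up about 11 points against Kauermann-Carroll with z (77.5% − 66.6%), which is the price of holding type I error near 5% instead of about 8.5%.

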3.5 Data Sources

Data will come from the following sources:

1. Patient participants: The 1,160 patients will complete structured interviews, either in-person or via phone, with trained interviewers at baseline, 3, 6 and 12 months. Research interviewers will also measure blood pressure, blood glucose, height, and weight.
2. Qualitative interviews with patients: Additional information on acceptability of the depression treatment program will be gathered via in-depth interviews with a subset of patients (n=8).
3. Clinical records: Information on depression treatment delivery and fidelity will be abstracted from clinical records.
4. Clinic director, Clinical Coordinator, provider, Friendship Bench counselor, SHARP research assistant, and MOH interviews: Information about implementation strategy and intervention acceptability and fidelity from in-depth interviews with clinic directors (n=6), Clinical Coordinators (n=6), providers (n=12), Friendship Bench counselors (n=6), SHARP research assistants (n=6), and MOH officials (n=3). Cognitive interviews will be conducted with providers (n=8) and Friendship Bench counselors (n=4). Structured surveys will be conducted with providers, friendship bench counselors, and clinic leadership (n=200).
5. End point qualitative interviews at each of SHARP's study sites will focus on additional factors affecting implementation strategy fidelity like organization climate, organizational change, and barriers and facilitators to strategy implementation. Specifically, this information will be gathered from clinic directors (n=10), Clinical Coordinators (n=10), providers (n=10), and SHARP research assistants (n=10).

3.5.1 Record Availability

The site investigator will make all data abstraction documents and records readily available for inspection by the local IRB and the Office for Human Research Protections (OHRP) as requested.

4.0 STATISTICAL ANALYSIS PLAN

Analysis of implementation and effectiveness outcomes will be intent-to-treat comparisons between arms. Comparisons will be made using generalized estimating equation models with a log link and binomial error distribution to compare proportions. The design effect introduced by clinic-level randomization will be addressed using the bias-corrected robust variance estimate for GEE models recommended given the small number of clusters. A secondary, as-treated analysis will restrict the analysis to those who received a minimum

dose of the depression treatment program (e.g., at least three depression care management appointments).

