5.0 ETHICAL CONCERNs	16
5.1 Human Subjects	16
5.1.1 Institutional Review Board	16
5.1.2 Confidentiality, Risks, and Risk Minimization	16
5.1.3 Benefits to Participants	17
5.1.4 Costs and Compensation	17
5.1.5 Informed Consent	17
5.2 Adverse Event Reporting	18
5.3 Study Discontinuation	18
6.0 PUBLICATION AND DISSEMINATION OF RESEARCH FINDINGS	18
7.0 WORKPLAN	20
7.1 Project Management	20

8.0 BUDGET	21
9.0 REFERENCES	22

HISTORY OF PROTOCOL CHANGES

Version 1.0, 9 August 2018

- None to date.

Version 1.1, 07 November 2018

- Changed titled to: The Sub-Saharan Africa Regional Partnership (SHARP) for Mental Health Capacity Building – A Clinic-Randomized Trial of Strategies to Integrate Depression Care in Malawi
- Added sample size justification
- Revised objectives
- Updated list of sites
- Discussion of risks related to recording and to blood collection
- Removed “not” from “These recordings will NOT be identified with a code number” on pages 14 and 15

Version 1.3, 04 December 2019

- Changed patient interview follow-up schedule from 3 and 9 months to 3, 6 and 12 months

Version 1.4, 20 February, 2020

- Made follow-up schedule consistent across protocol (interviews during Year 3)
- Added to Year 3 qualitative interview population (added 6 Clinical Coordinators, 6 Friendship Bench counselors, and 6 SHARP research assistants to the existing population of 6 clinic directors, 6 providers, and 3 MOH administrators)
- Reduced sample size for patient qualitative interviews from 16 to 8

Version 1.5, 19 March, 2020

- Amended interview format to include phone calls

Version 1.6, 30 September, 2020

- Added to Year 3 qualitative interview population (added 6 more providers for a total of 12)

Version 1.7, 26 February, 2021

- Added to Year 3 cognitive interviews and structured surveys to evaluate providers' perceptions of stigma and acceptance towards individuals with mental health disorders.

Version 1.8, 1 September, 2021

- Added Year 4 qualitative interviews with hospital workers and SHARP research assistants following results of Year 3 qualitative interviews

Version 1.9, 11 November 2022

- Removed Dignitas International personnel from protocol team roster
- Updated statistical analysis plan to replace generalized linear models with generalized estimated equation models.

PROTOCOL TEAM ROSTER

UNC Principal Investigators

[name], MPH
UNC School of Public Health
Department of Epidemiology
[name]
[name]

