3.0 METHODOLOGY

We will conduct a clinic-randomized trial (RCT) to determine the best way to integrate evidence-based depression treatment into non-communicable disease (NCD) clinics in Malawi. We will compare implementation of depression treatment using (1) a basic implementation package vs. (2) an enhanced implementation package.

The basic implementation package will involve identifying an internal coordinator who is one of the full-time on-site providers at the clinic. The internal coordinator provides mentoring to peers and support to leadership in implementing the treatment program and aligning it with clinic priorities.

The enhanced implementation package will combine the internal coordinator with an external quality assurance committee. This committee will complete quarterly audits at the facility to evaluate compliance with the depression treatment protocol as well as providing

high-level support in implementing the treatment program through clinical expertise and limited on-site presence.

Clinics will be randomized 1:1 to receive either the basic or the enhanced implementation package. Clinics will then implement depression treatment as part of standard care at their NCD clinics. All patients at each clinic will receive that clinic's standard care.

To evaluate patient health outcomes, we will enroll a cohort of patients from each NCD clinic. (Sample size and inclusion criteria are below.) Participants will complete assessments at baseline and 6 and 12 months. Assessments will measure sociodemographics, depressive severity, self-reported health, and key medical, structural, and psychosocial factors including trauma history, intimate partner violence, other violence in the home, socioeconomic measures, coping, social support, self-efficacy, experiences of stigma related to mental health, medical and psychiatric comorbidity, and risk factors for hypertension and diabetes. Medical appointment attendance data will be abstracted from clinic records.

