3.2 Population

Patients at the participating NCD clinics who meet the following eligibility criteria will be invited to participate.

Inclusion criteria

1. Ages 18-65 years (antidepressant treatment considerations differ for those <18 or >65 years, and these age groups are expected to be very rare in the target clinics),
2. Current or new patient receiving care for either hypertension or diabetes from the NCD clinic at a study site listed in Section 3.1, and
3. Elevated depressive symptoms (PHQ-9 score ≥ 5).

Exclusion criteria

Patients will be excluded if they have a history of bipolar or psychotic disorder, or show emergent threat of self-harm.

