3.3 Duration

The Phase II RCT will occur during project years 2-4 (November 2018-October 2021). We will complete training for providers and staff in the two arms. We will initiate the two implementation strategies at all clinics and spend 24 months recruiting participants. Follow-up monitoring will extend an additional 12 months, through year 4.

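### Section 4.0 names no baseline covariate for the remission model. Prespecifying adjustment for baseline PHQ-9 is a cheap improvement; the unadjusted GEE is valid provided enrolment does not depend on arm.

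*Combined protocol and SAP*

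**What the plan says.** **Model.** Section 4.0 specifies intent-to-treat comparisons between arms: "Comparisons will be made using generalized estimating equation models with a log link and binomial error distribution to compare proportions". A bias-corrected robust variance handles clustering. No patient-level or clinic-level covariate is named, and nothing says that the unadjusted estimate is the only one intended.

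**Baseline severity.** Section 3.2 makes PHQ-9 an entry criterion, "Elevated depressive symptoms (PHQ-9 score ≥ 5", so every enrolled patient has a score. Section 3.0 also includes severity in the study interviews, baseline among them, without naming the instrument: "Assessments will measure sociodemographics, depressive severity, self-reported health".

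**Order of events.** Section 3.0: "Clinics will be randomized 1:1 to receive either the basic or the enhanced implementation package". Section 3.3: "We will initiate the two implementation strategies at all clinics and spend 24 months recruiting participants". Patients are therefore identified after their clinic is allocated and has begun. Section 3.2 admits both current and new clinic patients.

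**Difference between arms.** Both arms have an internal coordinator and deliver the depression programme. Only the enhanced arm adds an external committee: "This committee will complete quarterly audits at the facility".

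**Dates.** Section 3.3 gives the planned period: "The Phase II RCT will occur during project years 2-4 (November 2018-October 2021". The last entry in the history of changes, "Version 1.9, 11 November 2022", replaces generalized linear models with GEE.

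**The concern.** Randomising clinics does not by itself balance patients who are selected afterwards. If the audits changed how actively an enhanced-arm clinic identified depressed patients, the severity mix could differ by arm. Milder patients may remit more often, so the remission contrast would move with no treatment effect. A robust variance does not help, because it is the point estimate that shifts.

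Two lesser matters go with this. Baseline severity usually predicts remission, so leaving it out gives up some precision. And with 5 clinics per arm, adjusted and unadjusted estimates can differ noticeably, so an unstated choice between them is better settled before outcomes are seen by arm.

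**Working it through.** **Inputs from section 3.4.** Remission 40% and 55%; two-sided α 0.05; power 80%; ICC 0.02; retention 90%; 10 clinics of 116 patients.

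**1. The plan's own figure.**
- Individually randomised n per arm = (1.960 + 0.842)² × (0.40×0.60 + 0.55×0.45)/0.15² = 170.06.
- Analysed per clinic, with 5 clinics per arm = 170.06×0.98/(5 − 170.06×0.02) = 104.2.
- Enrolled per clinic = 104.2/0.90 = 115.8, rounded up to 116; total 1,160.

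The stated sample size reproduces exactly, with no covariate term.

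**2. Unadjusted power.** With m = 0.9×116 = 104.4:

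Var = Σ over arms of p(1−p)/5 × [0.02·b + 0.98·w/m]

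Here b and w are the fractions of between-clinic and within-clinic variance left after adjustment. With b = w = 1, Var = (0.4875/5) × (0.02 + 0.98/104.4) = 0.002865 and SE = 0.0535. Power is 80.0% with a normal reference and 69.1% with a t reference on 8 df.

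**3. Gain from adjustment.** Assumptions, not in the documents: half of patients enter at PHQ-9 5-9, and their remission is 20, 30 or 40 points higher than that of the rest. Then R² = 0.25×gap²/(0.475×0.525) = 0.040, 0.090, 0.160. With severity ICC s, b = 1 − R²·s/0.02 and w = 1 − R²·(1−s)/0.98.

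| Gap (points) | s = 0: t8 (normal) | s = 0.02: t8 (normal) |
|---|---|---|
| 20 | 69.6% (80.5%) | 70.8% (81.6%) |
| 30 | 70.3% (81.2%) | 73.1% (83.6%) |
| 40 | 71.3% (82.1%) | 76.4% (86.4%) |

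On the t reference the gain is 0.5-2.2 points at s = 0 and 1.7-7.3 points at s = 0.02. It is small at s = 0 because about 68% of the variance, 0.02/(0.02 + 0.98/104.4), lies between clinics and is then untouched.

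**4. Possible loss.** If adjustment raised between-clinic variance by 10% (b = 1.10, w = 1 − R²), t8 power would be 66.7%, 67.4% and 68.3%. The rise that just cancels the gain is R² × (0.98/104.4)/0.02, about 1.9%, 4.2% and 7.5%.

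**5. Simulation with enrolment independent of arm.** Set-up: 10 clinics of 104 patients, outcome ICC 0.02, remission stepping down at PHQ-9 10; log link, Poisson working variance, independence working correlation, Kauermann-Carroll correction, t on 8 df, linear PHQ-9 term; 4,000 trials per scenario.
- Power, unadjusted to adjusted, for gaps 20, 30, 40. s = 0: 66.1 to 66.2, 66.1 to 67.3, 66.2 to 67.6%. s = 0.02: 66.7 to 67.5, 66.4 to 69.3, 66.6 to 72.2%.
- Type I error: 4.4-5.0% unadjusted, 4.5-5.1% adjusted. Both analyses hold their size.

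The simulated gains (0.1-1.4 and 0.8-5.6 points) are somewhat below the formula.

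**6. Hypothetical differential recruitment, no true effect.** Let the share at PHQ-9 5-9 differ by 10 points between arms. The remission contrast then moves by 0.10 × (20 to 40) = 2-4 points, against a target of 15.
- Simulated mean log risk ratio, unadjusted (gaps 20 and 40): 0.041 and 0.085, that is risk ratios of 1.04 and 1.09.
- Adjusted with a linear PHQ-9 term: 0.016 and 0.031, that is 1.02 and 1.03. With a term for 5-9 versus 10 or more, about zero. The linear term falls short because the simulated risk is a step.
- Unadjusted type I error: about 5%, 7% and 10% for gaps 20, 30 and 40 (1,200 trials each). A separate run at gap 30 (3,000 trials) gave a risk ratio of 1.08 with 8.3% rejection, against about 1.00 with 5.0% when adjusted for severity group.

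**The case against.** The strongest case against acting is that this is a preference. The unadjusted GEE holds its size when enrolment does not depend on arm. The power gain is then slight, and its upper end needs both a 40-point remission gap and a severity ICC of 0.02, whereas section 3.4 gives that ICC only for the outcome. Adjustment could also cost a little power. PHQ-9 is measured after strategy start and current patients may enrol, so the score may absorb part of any effect that preceded enrolment. All of this stands, and it keeps the priority modest. It does not remove the reason to settle the choice in advance when the covariate is already collected.

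A reader might infer that the planned analysis is biased or invalid. The documents do not support that. Both arms use the same PHQ-9 cut-off and deliver the same programme, and no text shows that recruitment differed by arm. Arm-independent recruitment is not described either, but section 3.1 is missing from the text available, so any randomisation or recruitment detail there could not be checked.

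A reader might also infer from the November 2022 revision that the model was chosen after results were seen. The October 2021 end is only a planned date, the logged change concerns the type of model and not covariates, and the documents do not say whether outcomes had been compared by arm.

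**Conclusion.** The point holds as a cheap improvement of modest priority. Section 4.0 leaves a collected predictor of remission unused and does not say whether an adjusted estimate will be reported. The unadjusted GEE is conditionally valid: chance imbalance between clinics is in its variance, but a severity difference caused by recruitment after allocation is not.

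The likely benefit is small: about 0.5-2 power points if clinics do not differ in severity, and up to about 7 if they do (severity ICC 0.02). The protection against differential recruitment matters more in principle, but its size is unknown. The risk ratio of 1.04-1.09 and type I error of about 5-10% illustrate an assumed 10-point shift; they are not evidence that one occurred. Adjustment would remove most or all of such a shift, depending on the form of the PHQ-9 term. The mild share, the remission gaps, the severity ICC and the shift are all assumptions from outside the documents.

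**What to change.** In section 4.0:

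- Prespecify a remission GEE with arm and individual baseline PHQ-9 at each remission time point analysed (3 months in section 3.4; 6 and 12 months in section 2.1). Keep the log link and the bias-corrected robust variance, and report the unadjusted estimate alongside.
- Enter PHQ-9 flexibly, for example as a continuous term plus an indicator for 5-9 versus 10 or more. Use one source for all patients: the baseline-interview score, or the eligibility score if that is the only one recorded.
- Name a Poisson working variance as the fallback if the log-binomial fit does not converge.
- Tabulate baseline PHQ-9 by arm and clinic.
- Document, with a date, that the choice preceded any comparison of outcomes by arm. If that cannot be shown, keep the unadjusted estimate as leading and label the adjusted one a sensitivity analysis.
- State that adjustment covers measured severity only, and that a score taken after strategy start may absorb part of an earlier effect.

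The cost is a few sentences and one table, with no new measurement. The remaining downside is a possible small loss of power if adjustment raises between-clinic variance.

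### With five clinics per arm, a remission test that holds two-sided 5% has about 67–69% power at the planned inputs, not 80%, and Section 4.0 does not fix which test is used

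*Combined protocol and SAP*

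**What the plan says.** Section 3.4 lists its design assumptions as "1) two-sided statistical significance tests; (2) Type I error $\alpha=0.05$; (3) power ($1-\beta$) of 80" percent, with an ICC of 0.02, 40% remission under the basic package and 90% retention. It sets the target this way: "A difference of 15 percentage points or more in depression remission in the enhanced arm relative to the basic arm would be clinically meaningful". It concludes that "we will enroll 116 participants per clinic from 10 clinics, or 1,160 participants overall". On the ICC it notes that "clinic-level ICCs normally range from <<0.01 to 0.04". Section 3.0 randomizes clinics 1:1, so there are five per arm.

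Section 4.0 compares proportions by GEE with a log link and binomial errors. Its only provision for the few clinics is that the design effect "will be addressed using the bias-corrected robust variance estimate for GEE models recommended given the small number of clusters". No section names the correction, the reference distribution, its degrees of freedom or the working correlation.

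The change history dates the sample size justification to version 1.1 (November 2018). The entry for version 1.9 (November 2022) reads "Updated statistical analysis plan to replace generalized linear models with generalized estimated equation models". The sample size was therefore set before the present analysis method.

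**The concern.** Two things are missing.

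- **The power figure.** It appears to treat the between-clinic standard error as known. With five clinics per arm that error is estimated on 8 degrees of freedom, and a valid test must pay for this.
- **The test.** A bias-corrected variance repairs the standard error on average, but it does not set the critical value. Several corrections exist, and each can be paired with 1.96 or with a t quantile. Two analysts could both follow Section 4.0 and reach opposite conclusions from the same data.

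Remission is the outcome on which the trial is powered. If the test holds 5%, a null result would be over-read as coming from an 80%-powered trial. If power stays near 80%, it is because the false-positive rate is above 5%.

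**Working it through.** **Inputs (Sections 3.0 and 3.4).** Two-sided α = 0.05; power 80%; p₁ = 0.40; p₂ = 0.55; ICC 0.02; 5 clinics per arm; 116 enrolled per clinic; 90% retention, so m = 0.9 × 116 = 104.4 evaluable.

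**1. Reproduce the plan's figure.**
- Without clustering: n = [0.40×0.60 + 0.55×0.45] × (1.960 + 0.8416)² / 0.15² = 170.06 per arm.
- With design effect 1 + (m − 1)×0.02 and 5 clinics per arm: m = n(1 − 0.02)/(5 − 0.02n) = 104.24.
- Enrolled: 104.24/0.90 = 115.8, rounded up to 116.

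The match is exact, so the 80% rests on normal quantiles.

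**2. What a bias-corrected variance becomes here.** Assume equal clinics and a model with arm only. Let SS be the within-arm sum of squares of the five clinic estimates. Each clinic has leverage 1/5, so the variance of an arm's mean is:
- Kauermann-Carroll (KC): SS/(25×0.8) = SS/20
- Mancl-DeRouen (MD): SS/(25×0.8²) = SS/16

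Both are fixed multiples of the same SS. KC is the ordinary two-sample variance of clinic means, and the MD standard error is √(20/16) = 1.118 times the KC one. Once calibrated to 5%, both give the same t test on 10 − 2 = 8 df.

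**3. Type I error of each reading.**
- KC with 1.96: P(|t₈| > 1.960) = 8.6%
- MD with 1.96: P(|t₈| > 2.191) = 6.0%
- KC with t₈: P(|t₈| > 2.306) = 5.0%
- MD with t₈: P(|t₈| > 2.578) = 3.3%

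**4. Power at ICC 0.02.** The design effect is 1 + 103.4×0.02 = 3.068, so the effective n per arm is 522/3.068 = 170.1.
- Risk difference: ncp = 0.15/√(0.4875/170.1) = 2.802
- Log risk ratio: ncp = ln(0.55/0.40)/√[(0.60/0.40 + 0.45/0.55)/170.1] = 2.728

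| Test | Type I error | Power, risk difference | Power, log risk ratio |
|---|---|---|---|
| Normal, SE treated as known | not applicable | 80.0% | 77.9% |
| KC with 1.96 | 8.6% | 79.2% | 77.3% |
| MD with 1.96 | 6.0% | 72.6% | 70.4% |
| KC with t₈ | 5.0% | 69.1% | 66.8% |
| MD with t₈ | 3.3% | 60.4% | 57.9% |

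About 2 points of the lower figure come from the log scale rather than from the few clinics.

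**5. Check by simulation.** Beta-binomial data, 104 per clinic, log-link GEE, 200,000 replicates, ICC 0.02. KC with t₈ has size 5.0% and power 66.8%. KC with 1.96 has size 8.6% and power 77.6%. An exact clinic-level permutation test over the 252 unrestricted 5:5 allocations (20,000 replicates) has size 4.3% and power 64.6%.

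**6. Sensitivity of KC with t₈.**

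| ICC | Power | Difference detectable at 80% power |
|---|---|---|
| 0.01 | 83–85% | 14.0–14.3 points |
| 0.02 | 67–69% | 17.1–17.7 points |
| 0.04 | 46–48% | 21.9–23.2 points |

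Power reaches 80% at an ICC of 0.0131 (risk difference) or 0.0119 (log risk ratio). At ICC 0.02 with 10 clinics it needs about 432 or 808 enrolled per clinic, respectively.

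**The case against.** - **The shortfall is conditional.** The lower part of the protocol's own ICC range meets the target: power is 83–85% at 0.01. Much larger clinics would also meet it. This stands, and the conclusion is limited to ICC 0.02 and 116 per clinic. Those are the values on which the 80% claim rests.
- **The 67–69% is one option, not a constant.** Other tests at or below 5% have less power: about 65% for the permutation test and 58–60% for MD with t₈. This is right, and it makes 67–69% the favourable end for a test that holds 5%.
- **The time point is unsettled.** Section 3.4 ties 90% retention to a 3-month primary outcome, while the hypotheses in Section 2.1 concern 6 and 12 months. At 80% retention power is 65–67%, so the conclusion hardly moves.
- **The plan already recognises the few-clusters problem and never says it will use 1.96.** True. The 8.6% is what the text permits, not what it prescribes.
- **The working correlation makes no difference with equal clinics.** True for an arm-only model. It matters only if clinic sizes turn out very unequal.
- **Restating power may come too late.** By the dates in Section 3.3 the design may be past changing, and a null result should be read mainly from its confidence interval. That lowers the value of the 3.4 change. It does not touch the 4.0 change, which decides whether 5% is held and how wide that interval is.

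**Conclusion.** The concern holds. At the protocol's own ICC, clinic size and retention, no test that holds two-sided 5% delivers the stated 80%. Power is about 67–69%, and the difference detectable at 80% power is about 17–18 points rather than 15. Section 4.0 as written also allows tests with type I error from 3.3% to 8.6% and power from 58% to 79%.

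These figures assume equal clinic sizes, an arm-only model at a single time point and 8 degrees of freedom. Covariates at clinic level, or stratified or matched randomization reflected in the analysis, would change the degrees of freedom. The type I figures are conditional on the reading of Section 4.0. The same rule governs fidelity (H1) and hypertension and diabetes control (H3), but their clinic denominators are not given, so no figure is claimed for them.

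**What to change.** **Section 4.0.** Name the correction, reference distribution and working correlation, choosing a test that holds about 5%, and fix them before outcomes by arm are seen. For example:

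> Wald tests and 95% confidence intervals use the Kauermann-Carroll variance with an exchangeable working correlation, referred to a t distribution with degrees of freedom equal to clinics minus cluster-level parameters (8 for an arm-only model).

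If clinic sizes vary widely (a coefficient of variation of 0.6 is assumed here, not taken from the protocol), simulated type I error of this example is 5.4–5.8% with exchangeable and 6.5–6.8% with independence weights. Mancl-DeRouen with t₈ stays at or below 4.1% throughout and is a defensible alternative, at a cost in power. Add a clinic-level permutation test over the actual allocation set as a sensitivity check.

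**Section 3.4.** Add:

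> With this test, power for 40% vs 55% at 116 per clinic is about 67–69% at ICC 0.02 (83–85% at 0.01, 46–48% at 0.04); the difference detectable with 80% power at ICC 0.02 is about 17–18 points.

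**Cost.** Two sentences, the sensitivity check and a small programming change, with no change to enrolment. Confidence intervals with KC and t₈ are about 18% wider than with KC and 1.96 (2.306/1.960), 5% wider than with MD and 1.96 (2.306/2.191), and 11% narrower than with MD and t₈ (2.306/2.578). The stated power becomes less favourable. Regaining 80% at ICC 0.02 with 10 clinics would take roughly 430–810 patients per clinic, so disclosure is the practical course.
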